19.2 Use of Data and Publications

Information regarding the study and study data will be made available via publication on clintrials.gov.

All data and results and all intellectual property rights in the data and results derived from the study will be the property of NiTiNotes, who may utilize the data in various ways, such as for submission to government regulatory authorities or disclosure to other investigators, educational, further product development and marketing uses.

The investigator, while free to utilize data derived from the study for scientific purposes, must discuss any publication with the sponsor prior to release and obtain written consent of the sponsor on the intended publication. The sponsor recognizes the right of the investigator to publish the results upon completion of the study. However, the investigator must send a draft manuscript of the publication or abstract to the sponsor 45 days in advance of submission in order to obtain approval prior to submission of the final version for publication. This will be reviewed promptly and approval will not be withheld unreasonably. In case of a difference of opinion between the sponsor and the investigator(s), the contents of the publication will be discussed in order to find a solution which satisfies both parties.

Disclosure of involvement in a publication (e.g., sponsor of the study; collection, analysis, and interpretation of data; professional writing assistance) must be as specified by journal-specific policies, submission requirements, and prevailing editorial standards, in addition to those specified by International Committee of Medical Journal Editors. Authors must ensure that an acknowledgement/disclosure statement is included in the body of the manuscript for NiTiNotes to review for accuracy. All authors must also disclose financial or personal affiliations that could be considered conflicts of interest as per journal requirements.

	Title: Evaluation of EndoZip™ System (AS) in Obese Patients who failed to reduce weight with non-surgical weight-loss methods		
Document No: CL00003	Rev: 1.0		Page: 68 of 83

21.0 Appendix A: Post Procedure Regime

21.1 Pre-Procedure diet

- Patients will follow a clear liquid diet starting 24 hours prior to scheduled arrival time for the procedure
- Patients will be NPO after midnight the night before the procedure. (exception - small sips of water for medication)

21.2 Post Procedure Diet

At each individual session, dietitians will perform a diet recall and exercise recall to determine compliance with the diet recommendations and the exercise goals. The dietitian will discuss the barriers patients have that may be preventing them from achieving their diet recommendations and their exercise goals. In conjunction with the patient, the dietitian will set 1-3 goals for the patients to work on before the next session.

The patient will be under the following diet regime from Day 0 to Week 8 Post Procedure (PP, Table 1)

Table 1. Diet Progression

Phase	Duration	Types of Liquids or Foods	Protein Goal	Notes
Phase 1: Clear liquid diet	PP Day 1 to PP Day 3	Clear Liquids only	60-80 gm	
 • Will need protein supplement to maintain protein goals • Focus on protein intake, adherence to clears, and sufficient liquids to avoid dehydration total calories may be low
Phase 2: Full liquid diet	PP Day 4-PP Day 14	Full Liquids and Clear Liquid	60-80 gm	
 • Will need protein supplements to maintain protein goals • Still need to focus more on protein intake and sufficient liquids to avoid dehydration • Total calories may be low, but if patient can maintain activities, hydration, and energy level do not force additional intake

	
Title: Evaluation of EndoZip™ System (AS) in Obese Patients who failed to reduce weight with non-surgical weight-loss methods
		
Document No: CL00003	Rev: 1.0	Page:	70 of 83

Phase	Duration	Types of Liquids or Foods	Protein Goal	Notes
Phase 3: Semi-Liquid (Pureed) Diet	PP Day 15 to PP Day 42	Pureed Food, Full Liquids, and Clear Liquids	60-100gm (higher protein range for tall patients and men)	
 • May still need protein supplements • Eat pureed meals slowly – discomfort can occur quickly 
Avoid fluid intake within 30 min of a meal

Phase 4: Semi-Solid Diet	PP Week 6-PP Week 8	Add soft foods that can be easily chewed	60-100 gm (higher protein range for taller patients and men)	
 • Still continue to eat slowly and chew food well • Continue to drink between meals and stop 30 min before a meal
Phase 5: 1200 – 1500 Calories Diet				

21.3 Phase 1: Clear Liquids Only

Water-based diet for 2-3 days after the procedure.

Recommendation for Patients:

- You can start Clear Liquids when awake after the procedure.
- Clear liquids are liquids that you are able to see through when you hold up a glass of the liquid to light. Examples include sugar-free and room temperature water, light tea, chamomile, herbal teas, and Jelly.
- They are easily digested and leave no undigested residue in your intestinal tract.
- Medium temperature or room temperature liquids may be better tolerated than extremely cold and extremely hot liquids after the procedure.
- For adequate protein on a clear liquid diet, you NEED to supplement.
- Aim for 60g of protein per day and 48 fluid ounces per day. You can purchase protein powder online
- Consume 2 tablespoons/30 cc of clear liquids every 15 minutes in order to maintain hydration.
- Use a timer to accurately track 15 minutes and avoid dehydration.
- Avoid caffeine and alcohol for 1 month, as these can cause stomach irritation and dehydration as you heal.
- Avoid sugary drinks, which can lead to diarrhea.
- Avoid carbonated beverages for 1 month, along with using straws, as this can lead to the swallowing of more air.
- Do not gulp liquids – be sure to sip.
- Avoid chewing gum to prevent taking in more air as well.

	Title: Evaluation of EndoZip™ System (AS) in Obese Patients who failed to reduce weight with non-surgical weight-loss methods	
Document No: CL00003	Rev: 1.0	Page: 71 of 83

21.4 Phase 2: Full Liquid Diet

Recommendation for Patients:

- All liquids should pour off a spoon.
- Consume foods that are liquid or semi-liquid at room temperature.
- You may not feel hungry most of the time and find it difficult to eat even three times a day.
- Small portions sizes are essential!
- Eat your meals slowly. Allow for 20-30 minutes per meal.
- Drink water or zero-calorie fluids throughout the day.
 - Your goal is 1.5 liters of fluids a day, working up to 2 liters of fluids a day.
 - Drink between meals but not right before or during.
 - NO straws. You can suck up too much air and cause discomfort.
 - Sip, sip, sip.

Recommended Foods:

- Any of the food from Stage 1-Clear Liquids
- Milk or milk alternatives (low-fat or non-fat is preferred).
- Creamed soups
- Broth based soups run through the blender, no lumps or bumps
- Protein supplement drinks
 - With at least 15g protein and less than 3g of sugar.
 - Popular brand: Unjury Protein or Premier Protein
- Thinned hot cereal:
 - Cream of wheat
 - Instant oatmeal
- Thinned mashed potatoes (thinned with chicken, vegetable, or beef broth)
 - Flavoring ideas:
 - Thyme, oregano, basil, garlic, onion powder
 - Packaged gravy mix
- Low-sugar yogurt or sugar-free pudding
- Low-sugar light, drinkable yogurt

Between Meal Liquids: (low calorie, less than 10 Calories per 8 fluid ounces)

- Water
- Sugar-free flavored drink packets
- Broth
- Decaffeinated coffee or tea – fat free creamer and sugar substitute are OK
- Tomato or vegetable juice (limit to 6 fluid ounces per day)

Sample Meal Plan:

	Title: Evaluation of EndoZip™ System (AS) in Obese Patients who failed to reduce weight with non-surgical weight-loss methods	
Document No: CL00003	Rev: 1.0	Page: 72 of 83

Between meals liquids (low calories, less than 10 calories per 220 cc liquids – 1 cup)

- Water
- Sugar-free flavored drink packets
- Decaffeinated coffee or tea – fat free creamer and sugar substitute are OK
- Tomato or vegetable juice (limit to 175 cc fluids per day)

Breakfast – 120ml of Semolina / rice cream

Snack – 120ml of 1% milk with a spoon of protein powder / other protein drink

Lunch – 120ml creamed soup

Snack – 120ml of 1% milk with a spoon of protein powder / other protein drink

Dinner – 120ml filtered chicken soup

Snack – 120ml of 1% milk with a spoon of protein powder / other protein drink

21.5 Phase 3: Semi-Liquid (Pureed) Diet

Recommendation for Patients:

This diet includes:

- Foods that do not need much chewing.
- Typically, ground, pressed, blended, or sieved to the consistency of a soft creamy paste or thick liquid.
- Continue drinking fluid between your meals, but stop 30 minutes before your meal and start again 60 minutes after your meal.

Recommended Foods:

- All foods from the clear liquid and full liquid diets
- Low-sugar yogurt
- Low-fat white cheese
- Scrambled eggs
- Pureed beef, chicken, or turkey
- White fish mashed finely with a fork
- Tuna mashed finely with a fork
- Mashed or pureed potatoes/sweet potatoes
- Pureed cooked butternut squash

	Title: Evaluation of EndoZip™ System (AS) in Obese Patients who failed to reduce weight with non-surgical weight-loss methods		
Document No: CL00003	Rev: 1.0	Page: 73 of 83	

- Pureed cooked spinach, carrots, green beans
- Tahini
- Avocado
- Banana

Sample Meal Plan:

Snacks (mid morning and mid afternoon)

- 120 ml skimmed milk
- 125 g low fat white yogurt / cheese
- 1 teaspoon almond butter
- 1 teaspoon of natural peanut butter
- 1 spoon of tahini

Breakfast – 1 scrambled egg + 0.5 cup of low fat white cheese + decaffeinated coffee/tea

Snack – 130g Fruit puree

Lunch – 100-150 g Pureed beef, chicken, or turkey + 100 ml vegetable puree (chard, spinach, lettuce, zucchini, broccoli)

Snack – 125 g low fat white yogurt

Dinner – 120ml filtered chicken soup

Snack – 120ml of 1% milk with a spoon of protein powder / other protein drink

21.6 Phase 4: Semi-Solid Diet

Table 2. Phase 4 and 5: Protein goals and Maximum calorie amounts

Start Weight	68-89		90-112		113 and above	
	Calories or Protein	kcal	protein	kcal	protein	kcal
Amount	1200	60-80	1300	70-90	1500	80-100

Both calories and protein need to be tailored to the patient. The calories listed are the maximum goals – patients should not eat over this amount, but can eat less. Many patients will eat less than these calorie levels in the first few months after the procedure.

If patients are eating less than the amounts listed below, have no evidence of dehydration and

	Title: Evaluation of EndoZip™ System (AS) in Obese Patients who failed to reduce weight with non-surgical weight-loss methods	
Document No: CL00003	Rev: 1.0	Page: 74 of 83

have good energy levels they do not need to force additional calorie intake. **Forcing food/volume can lead to patient discomfort / adverse events and should be avoided.**

Recommendation for Patients:

This diet includes:

- Foods that are easily chewed and swallowed.
- Avoid foods that are hard like nuts, popcorn, or seeds, stringy like cooked onions and cooked bell peppers, or tough like dried fruit or smoked meats.
- Avoid foods that can cause gas like broccoli, Brussel sprouts, cabbage, cauliflower, bell peppers and onions.
- Vegetables should still be cooked in this phase and all food should be chewed thoroughly.

Recommended Foods:

- Anything in the prior diet phases
- Moist and tender meats
- Cooked or canned fruits
- Banana
- Avocado
- Tahini
- Cooked vegetables
- Plain, white rice, pasta-no more than 1/3 of a cup
- Refined wheat bread
- Homemade hummus

Snacks (mid morning and mid afternoon)

- 120 ml skimmed milk
- 125 g low fat white yogurt / cheese
- 25g light Emmental cheese
- 1 teaspoon almond butter
- 1 teaspoon of natural peanut butter
- 1 spoon of tahini / avocado spread
- 3 spoons smooth homemade hummus
- 130g Fruit puree

Sample Meal Plan:

Breakfast – 1 scrambled egg + 25g light Emmental cheese + decaffeinated coffee/tea

Snack – 130g Fruit puree

	Title: Evaluation of EndoZip™ System (AS) in Obese Patients who failed to reduce weight with non-surgical weight-loss methods	
Document No: CL00003	Rev: 1.0	Page: 75 of 83

Lunch – 160 g fish pureed or well chopped + Ricotta 70 g / Philadelphia light 60g + 110 g mashed or pureed potatoes/sweet potatoes

Snack – 120ml of 1% milk with a spoon of protein powder / other protein drink

Dinner – 20 g Semolina / rice cream / small pasta in 100ml vegetable broth + 5 g parmesan cheese

21.7 Phase 5: 1200 – 1500 Calories Diet

Recommendation for Patients:

This diet includes:

- 1,200-1,500 kcal/day diet
- 60-80g of protein/day (20g of protein at breakfast)
- Eat small amounts, several times a day.
- Set utensils down in-between bites.
- Eat slowly, and stop at first sign of fullness.
- Chew foods thoroughly.
- Drink non-caloric beverages, avoid drinking gassy beverages, and drink in-between meals.

The following menu is designed according to the following calorie distribution:

- Breakfast – 200 -300 calories
- Snacks - 100 calories
- Lunch – 500 - 600 calories
- Snacks - 100 calories
- Evening – 300 - 400 calories

Sample Meal Plan:

Breakfast:

1 cup of low fat white yogurt (you can use yogurt enriched with protein 20 grams of natural protein) + half a cup of freshly cut fruit, 5 almonds / nuts

OR

	Title: Evaluation of EndoZip™ System (AS) in Obese Patients who failed to reduce weight with non-surgical weight-loss methods	
Document No: CL00003	Rev: 1.0	Page: 76 of 83

2 slices of light bread made from rye / spelled / 3 slices of cracker made from rice / buckwheat / corn (each up to 30 calories) / a half pita bread made from whole wheat / spelled + 1 spoon of white cheese 5% + hard-boiled egg + slices of vegetable (tomato / cucumber / red pepper) and leaf . lettuce

OR

3 spoons oatmeal + 0.5 cup of skimmed milk / herbal drink + 0.5 cup of water + chopped fresh banana and a little cinnamon

Snacks:

1.5 cup melon / watermelon cubes or other fresh fruit (1 medium unit)

OR

2 spoons white cheese 5% with fresh vegetables (5 cherry tomatoes, cucumber + 0.5 carrot)

Noon:

150 g baked salmon (can be used with herbs and lemon) / chicken breast + 3 spoons whole rice / quinoa / medium sweet potato + a cup of green beans in tomato sauce / a small bowl of (volume of a cup) vegetable salad with 1 teaspoon of olive oil / 1 spoon avocado

OR

120 grams of tofu cubes + 0.5 cup of cooked rice noodles or quinoa noodles + 2 cups of stir-fried vegetables (such as carrots, celery, mushrooms, onions, cabbage, cauliflower, broccoli ...) - for the sauce - 2 spoons soy sauce and 1 spoon of olive oil

Snacks:

Energy snack up to 100 calories / 1 date palms or 1 fresh fruit + 4 walnut or almond halves / Ice cream up to 100 calories / 2 crackers (up to 30 calories per unit) + a teaspoon of jam / honey on each cracker

Evening:

Omelet (1 egg) with herbs (onion, parsley, rocket, spinach) + 2 spoons cheese / white cheese 5% with vegetable salad + quarter avocado + 2 slices light bread / 1 slice of bread made from whole wheat / spelled / rye

OR

Tuna salad: 50 grams (one third of a box) tuna in water + hard-boiled egg + vegetable salad with a seasoning of 1 teaspoon of olive oil, half pita bread from spelled / whole wheat (up to 100 calories per pita)

OR

	
Title: Evaluation of EndoZip™ System (AS) in Obese Patients who failed to reduce weight with non-surgical weight-loss methods
		
Document No: CL00003	Rev: 1.0		Page: 77 of 83

1 cup of low fat white yogurt (you can enriched with natural-flavored protein) + whole apple + half pear + half nectarine + 2 flat spoons of granola without added sugar + 1 teaspoon of chia seeds

21.8 General Instructions

The information supplements the diet plan (divided into progressive phases) described above. They have been inserted to help operated patients to change their eating habits in order to reduce complications and side effects after the EndoZip procedure.

- **The re-feeding phase duration (respecting the indicated times)** will be strictly related to individual tolerance. If the introduction of new foods or foods with a different consistency might determine excessive gastric filling or vomiting, **please return to previous PHASE diet for 2-3 days.**
- **Eat slowly**, chewing your food well and stopping between one bite and the next. The meal must last at least 30-40 minutes.
- **Stop eating as soon as you feel full** (regardless of the amount of food ingested). Insisting would cause vomiting.
- **Start lunch and dinner with the protein dish** to ensure adequate protein intake during weight loss; then continue the meal with vegetables, fruit and finally the first course.
- Avoid eating and drinking at the same time.
- Do not induce vomiting.
- Eat the evening meal at least 2 hours before bedtime, to avoid the onset of gastroesophageal reflux.
- Drinks should be taken at least half an hour after the meal (before or after).
- Drink, initially, at least 1 liter of water during the day, only natural, in small sips. Tea, chamomile, barley, preferably decaffeinated coffee, herbal teas as long as they are sugar-free or using natural sweeteners based on Stevia are also allowed.
- **Avoid the consumption of carbonated, sugary, alcoholic and spirits drinks.**
- Vegetables should not be eaten in the first few weeks; they will then be reinserted gradually and in small quantities in the form of pureed vegetables or finely chopped.
- **Avoid the consumption of foods containing simple sugars and fats** (sweets, jams, honey, croissant, chocolate, ice cream, dried and canned fruit, fruit juices, spicy cheeses, sausages, sauces and various condiments).
- Avoid foods that are too spicy, too hot or too cold.
- In the final phase, divide up the meals of the day respecting the times (3 main meals + 1 mid-morning and mid-afternoon snack). Any changes must be agreed with the doctor.

	Title: Evaluation of EndoZip™ System (AS) in Obese Patients who failed to reduce weight with non-surgical weight-loss methods		
Document No: CL00003	Rev: 1.0	Page:	78 of 83

- **In case of constipation** make sure to introduce an adequate supply of water. However, it is possible that the doctor will recommend taking laxatives.
- Gradually increase physical activity (after consulting your doctor and based on your physical condition), so as to preserve muscle mass in conjunction with weight loss.

21.9 Physical Activity

For patients who exercised regularly (defined as at least 3 days per week for at least 30 minutes per session) before the procedure can return to exercise as tolerated once they are at least on a full liquid diet and have no post-procedure symptoms. For patients who have never exercised before, consider the following exercise titration in Table 2 after the patient has advanced to a pureed diet and their post-procedure symptoms have resolved.

1. The recommended exercise is at least moderate intensity exercise (brisk walk). High intensity training and high intensity interval training are also acceptable. Strength training is also encouraged
2. Goals: after return to exercise or titration of exercise 150 minutes of at least moderate intensity exercise (e.g. brisk walk with moderate breathing) per week

Table 2. Exercise progression

Week Post procedure	Moderate Intensity Exercise Duration	Sessions Per Week
2 Weeks PP	15 minutes	3
3 Weeks PP	15 min	4
4 Weeks PP	20 min	4
5 Weeks PP	20 min	5
6 weeks PP	30 min	5

	Title: Evaluation of EndoZip™ System (AS) in Obese Patients who failed to reduce weight with non-surgical weight-loss methods			
	Document No: CL00003	Rev: 1.0	Page: 79 of 83	

22.0 Appendix B – Usability Questionnaire (filled-in by the physician)

1. How was it to remove the system from the pack maintaining its sterility?

Very Easy	Easy	Acceptable	Difficult	Very Difficult
5	4	3	2	1

2. How was the system setting up with respect to the followings?

a. Connect to the electricity

Very Easy	Easy	Acceptable	Difficult	Very Difficult
5	4	3	2	1

b. Connect to the vacuum pump system

Very Easy	Easy	Acceptable	Difficult	Very Difficult
5	4	3	2	1

c. Connect to the Endoscope system

Very Easy	Easy	Acceptable	Difficult	Very Difficult
5	4	3	2	1

d. Connect to the CO₂ system (if used)

Very Easy	Easy	Acceptable	Difficult	Very Difficult
5	4	3	2	1

N/A (if CO₂ not been used during the procedure)

3. How was the insertion of the scope into the EndoZip device?

Very Easy	Easy	Acceptable	Difficult	Very Difficult
5	4	3	2	1

	Title: Evaluation of EndoZip™ System (AS) in Obese Patients who failed to reduce weight with non-surgical weight-loss methods				
	Document No: CL00003	Rev: 1.0	Page: 80 of 83		

4. How was the system advancement to the stomach through the Overtube?

Very Easy	Easy	Acceptable	Difficult	Very Difficult
5	4	3	2	1

5. How was the maneuvering process within the stomach to the desired suturing location?

Very Easy	Easy	Acceptable	Difficult	Very Difficult
5	4	3	2	1

6. For insufflation, did you use the EndoZip CO₂ channel? Yes No

a. If No, how was the insufflation process using the endoscope insufflation channel?

Very Easy	Easy	Acceptable	Difficult	Very Difficult
5	4	3	2	1

b. If Yes, how was the insufflation process using the endoscope and the EndoZip CO₂ extra channel?

Very Easy	Easy	Acceptable	Difficult	Very Difficult
5	4	3	2	1

7. How was the overall management of the system's stopcocks, clamps and valves (vacuum and CO₂ insufflation)?

Very Easy	Easy	Acceptable	Difficult	Very Difficult
5	4	3	2	1

8. How was the overall management of the system's knobs (for proximal and distal articulation)?

Very Easy	Easy	Acceptable	Difficult	Very Difficult
5	4	3	2	1

	Title: Evaluation of EndoZip™ System (AS) in Obese Patients who failed to reduce weight with non-surgical weight-loss methods			
	Document No: CL00003	Rev: 1.0	Page: 81 of 83	

9. How easy was the activation of operation button? (suturing, tightening, clipping and cutting process)

Very Easy	Easy	Acceptable	Difficult	Very Difficult
5	4	3	2	1

10. How easy was the identification of suturing stage through the system user panel (LEDs)?

Very Easy	Easy	Acceptable	Difficult	Very Difficult
5	4	3	2	1

11. How was the Corset wire release process (before system retrieval)?

Very Easy	Easy	Acceptable	Difficult	Very Difficult
5	4	3	2	1

12. How was the system retrieval process?

Very Easy	Easy	Acceptable	Difficult	Very Difficult
5	4	3	2	1

General impression:

1. How was the general touch and feel working with the EndoZip system?

Excellent	Good	Acceptable	Difficult	Unacceptable
5	4	3	2	1

2. How was the use of EndoZip system, comparing to ESG alternatives?

Significantly Easier	Easier	Same	Inferior	Significantly Inferior
5	4	3	2	1

NiTINOTES	Title: Evaluation of EndoZip™ System (AS) in Obese Patients who failed to reduce weight with non-surgical weight-loss methods			
	Document No: CL00003	Rev: 1.0	Page: 82 of 83	

Please grade your agreement with the following statements:

3. I think that I would like to use this system frequently

Strongly Agree				Strongly Disagree
5	4	3	2	1

4. I thought the system was easy to use

Strongly Agree				Strongly Disagree
5	4	3	2	1

5. I think that I would need the support of a technical person to be able to use this system

Strongly Agree				Strongly Disagree
5	4	3	2	1

6. I found the various functions in this system were well integrated

Strongly Agree				Strongly Disagree
5	4	3	2	1

7. I found the IFU (Instruction For Use) very informative and provides sufficiently the information needed to perform the procedure

Strongly Agree				Strongly Disagree
5	4	3	2	1

Comments _____

	Title: Evaluation of EndoZip™ System (AS) in Obese Patients who failed to reduce weight with non-surgical weight-loss methods	
Document No: CL00003	Rev: 1.0	Page: 83 of 83

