9.2 Secondary endpoints

The following secondary endpoints will be evaluated:

1. Percent of excessive weight loss (%EWL) over 6 and 12 months.
2. Reduction of weight and waist circumference over 6 and 12 months.
3. Impact of EndoZip procedure on gastric motility at 6 months.
4. Changes in Weight-related Quality of Life (IWQOL) Questionnaire scores at 6 and 12 months.
5. Time analysis including procedure duration, anesthesia duration, patient recovery duration.
6. Change in comorbid conditions over 12 months evaluated by:
 - a. Blood pressure
 - b. Glucose, HbA1c
 - c. Lipid levels (Total Cholesterol, LDL-C, HDL-C, and triglycerides)
 - d. Sleep Apnea test
7. Physicians' satisfaction based on a questionnaire

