14.0 Statistical Analysis

14.1 Sample Size Determination

This is a pilot study that will include up to 45 patients; no statistical considerations were made to determine the sample size.

The first two (2) patients per site will be considered as run-in period, to compensate for any learning curve that may be required for the EndoZip performance evaluation.

Safety evaluation will include all enrolled patients.

	Title: Evaluation of EndoZip™ System (AS) in Obese Patients who failed to reduce weight with non-surgical weight-loss methods		
Document No: CL00003	Rev: 1.0	Page:	53 of 83

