14.6 Secondary Endpoints Analysis

Excess Weight Loss % (EWL%)

EWL% of patients at 1, 2, 6 and 12 month(s) by study group will be summarized with descriptive statistics with 95% confidence intervals.

The percent excess weight loss (%EWL) will be calculated as $(\text{Weight(BL)} - \text{Weight(Visit)}) / \text{ExcessWeight(BL)}$, where ExcessWeight(BL) is calculated as difference between the patient's baseline weight in kilograms and the kilograms at which the patient's BMI would be 25.

Change of Weight and Waist Circumference Over 12 Months from Baseline

Change from baseline in BMI at 1, 2, 6 and 12 month(s) by study group will be summarized with descriptive statistics with 95% confidence intervals.

Changes in Weight-related Quality of Life (IWQOL) Questionnaire at 12 months

IWQOL questionnaire records will be summarized by study groups will be summarized with descriptive statistics with 95% confidence intervals.

Time analysis

Time analysis including procedure duration, anesthesia duration, patient recovery duration will be evaluated and will be summarized with descriptive statistics with 95% confidence intervals.

Change in Comorbid Conditions

Clinically significant changes at 6 and 12 months in fasting plasma glucose and HbA1c concentrations, change in systolic and diastolic blood pressure, changes in plasma total cholesterol, low-density lipoprotein cholesterol and triglyceride concentrations, will be evaluated and will be summarized with descriptive statistics with 95% confidence intervals

Percentage of patients who had clinically significant change will be provided with 95% confidence interval.

Usability and Physicians' satisfaction

Physicians' satisfaction will be evaluated by a questionnaire will be summarized with descriptive statistics with 95% confidence intervals.

	Title: Evaluation of EndoZip™ System (AS) in Obese Patients who failed to reduce weight with non-surgical weight-loss methods		
Document No: CL00003	Rev: 1.0	Page:	56 of 83

The physicians will be asked to fill-in a dedicated questionnaire to include their feedback on the procedure.

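### The only usability item that compares EndoZip with ESG has labels that are not opposites (ease on one side, general standing on the other), so it does not measure one dimension

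*Combined protocol and SAP*

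**What the plan says.** Appendix B (section 22.0) is filled in by the physician who performs the procedure. Under its general impression heading, item 2 asks "How was the use of EndoZip system, comparing to ESG alternatives". The options run "Significantly Easier" (5), *Easier* (4), *Same* (3), *Inferior* (2), "Significantly Inferior" (1). Every rated item among the numbered items 1 to 12 of the same form uses a matched scale from *Very Easy* to *Very Difficult*.

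The questionnaire feeds the seventh and last secondary endpoint in section 9.2, "Physicians' satisfaction based on a questionnaire"; the synopsis version of that endpoint also names usability. Section 8.2 makes it a secondary objective. Section 14.6 gives the analysis: "Physicians' satisfaction will be evaluated by a questionnaire will be summarized with descriptive statistics with 95% confidence intervals". No threshold, test or rule for combining items is stated. Section 14.2.2 adds that categorical variables are summarised by count and percentage. On size, section 14.1 says that "no statistical considerations were made to determine the sample size".

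**The concern.** A bipolar rating scale works when its two ends are opposite poles of one attribute. Here the upper half names ease and the lower half names standing relative to ESG. A rating of 4 and a rating of 2 are therefore not equal and opposite answers to one question, and neither a mean nor a percentage over this item has a single meaning.

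What is at stake is limited but specific. The study has one arm, so this item is the only one on the form that sets EndoZip against ESG. The protocol describes the device as easy for the operator (sections 5.1.3, 6.1 and 7.1). A summary of this item is thus a likely source for any comparative usability statement, and readers would take it as a statement about ease.

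**Working it through.** The plan has no figure to reproduce. The check sets the labels side by side and then follows what they allow.

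**1. Balance of the codes.** There are two favourable options, one neutral and two unfavourable. The mean of the codes is (5 + 4 + 3 + 2 + 1) / 5 = 3, which is the neutral code. The numbers carry no built-in skew; the fault lies in the labels alone.

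**2. Which answer fits which operator.** Take ease and overall standing as two separate judgements against ESG, and read the labels literally.

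| Operator's view | Labels that could be ticked | Error if ease is the target | Error if overall standing is the target |
|---|---|---|---|
| A. Easier, and better overall | Easier | none | none |
| B. Harder, and worse overall | Inferior | none | none |
| C. Harder, equal overall | Same or Inferior | +1 if Same | −1 if Inferior |
| D. Equally easy, better for another reason | Same or Easier | +1 if Easier | −1 if Same |
| E. Equally easy, worse for another reason | Same or Inferior | −1 if Inferior | +1 if Same |
| F. Easier, worse overall | Easier or Inferior | −2 if Inferior | +2 if Easier |

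The target codes assumed are 4 for easier or better, 3 for equal and 2 for harder or worse. Groups C to F each have two defensible answers, and the form does not record which judgement the operator used. Errors of both signs occur whichever target is chosen, so the net direction cannot be read off the scale.

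**3. Illustrative size.** The shift in the item mean from one group is h × q × step, where h is the share of forms from that group and q the share of those taking the ill-fitting label. The documents give neither h nor q. Assume h = 10% to 30% and q = 25% to 100%:

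- one-step groups (C, D, E): 0.10 × 0.25 × 1 = 0.025 up to 0.30 × 1.00 × 1 = 0.30 points
- two-step group (F): twice that, 0.05 to 0.60 points
- q = 0: no shift

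**4. Two mirror-image examples.** Let the true answers be 30% unfavourable, 40% same and 30% favourable: 0.3 × 2 + 0.4 × 3 + 0.3 × 4 = 3.0.

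- All unfavourable operators are in group C, ease is the target, and they tick *Same*: 0.7 × 3 + 0.3 × 4 = 3.3. The unfavourable share falls from 30% to 0%.
- All favourable operators are in group D, overall standing is the target, and they tick *Same*: 0.3 × 2 + 0.7 × 3 = 2.7. The favourable share falls from 30% to 0%.

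Both are extreme cases. They also show that a frequency table alone does not repair the item, because the percentages are distorted as readily as the mean.

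**The case against.** The strongest reply is that this is a wording blemish in one item of the last-listed secondary endpoint of a descriptive pilot. Absolute difficulty is recorded properly elsewhere: the rated items among 1 to 12 have matched labels, general item 4 asks whether the system was easy to use, and there is a comments field. All of that is true, and it limits the point to the comparison with ESG.

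A reader might go further and infer that an operator who finds EndoZip harder has no answer, so that the score drifts upward in the sponsor's favour. The documents do not support this. Two unfavourable options exist. The stem asks about use, so *Inferior* can take in harder use. A favourable judgement on grounds other than ease also lacks a label. Section 13.3 allows a sponsor representative to attend the procedure, which makes reluctance to tick *Inferior* plausible, but nothing shows that it occurs or how often.

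A reader might also extend the point to two other items. General item 1, "How was the general touch and feel working with the EndoZip system", has one label (*Difficult*) that does not match its neighbours, but its options remain ordered, two of them are clearly unfavourable, and no mechanism for bias is apparent. Item 9, "How easy was the activation of operation button? (suturing, tightening, clipping and cutting process", rates the activation of one button, not the performance of four functions. Items 10 and 11 rate stage identification and wire release separately, device deficiencies are documented (section 15.10), and procedures are video-recorded (section 13.3). Splitting item 9 would be a preference.

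Finally, section 14.6 does not say that the item will be averaged, and section 14.2.2 already provides counts and percentages for categorical variables. The shifts in the mean are therefore only an illustration. What remains is that the labels are not opposites, and that this affects any summary of the item.

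**Conclusion.** The point holds as a measurement fault of minor weight. General impression item 2 does not measure one dimension, and operators whose view of ease differs from their overall view of the device may be classified inconsistently. That the labels differ in kind is plain from the form and needs no assumption. The size does: on assumed shares, 0.025 to 0.30 points on the 1 to 5 scale for a one-step misfit and twice that for a two-step one, in either direction, or nil if no operator takes an ill-fitting label. The documents do not locate the true value in that range or fix its sign. No claim of bias in favour of the device should be made from this item. The co-primary endpoints and the safety analysis do not depend on it.

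**What to change.** Relabel code 2 of general impression item 2 as *More difficult* and code 1 as *Significantly more difficult*. The item then measures ease throughout, in line with the matched labels of the rated items among 1 to 12, and groups C to F above each have one fitting answer. State in section 14.6 that this item is reported as counts and percentages, which follows the existing rule for categorical variables in section 14.2.2.

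The cost is a wording change to Appendix B and the matching eCRF page, made before the form is first used. No extra data, patients or visits are needed. If the form is already in use, report the counts under the labels as printed, with a note that the scale mixes ease and general standing and does not support a statement on relative ease.
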